5.2 Study Hypothesis

The safety and effectiveness of the FRED meets similar performance goal as that which was identified from a comprehensive analysis of the peer-reviewed published literature reporting the safety and efficacy of endovascular treatment of intracranial aneurysms with flow-diverter devices.

Efficacy hypotheses

The study is designed to compare the rate of the primary efficacy endpoint to a performance goal. The null and alternative hypotheses are:

Null hypothesis: $H_0: \pi_e \leq 45\%$

Alternative hypothesis: $H_A: \pi_e > 45\%$

where π_e is the proportion of subjects that are successes for the primary efficacy endpoint.

Safety hypotheses

The study is designed to compare the rate of the primary efficacy endpoint to a performance goal. The null and alternative hypotheses are:

Null hypothesis: $H_0: \pi_s \geq 25\%$

Alternative hypothesis: $H_A: \pi_s < 25\%$

where π_s is the proportion of subjects with primary safety endpoint events.

5.3 Study Description

The proposed study is a multi-center, prospective, single arm study with follow-up at 30 days (\pm 7 days), 180 days (\pm 30 days), and 12 months (+ 60 days, -30 days). The study includes five components:

- Screening period;
- Treatment period;
- 30-day clinical* follow-up visit;
- 180-day clinical* and angiographic follow-up visit;
- 12-month clinical* and angiographic follow-up visit.

* Clinical visit will include a physical and neurological exam. Ophthalmic examination will be performed if determined to be appropriate

5.4 Target Population

- Subjects with a single target intracranial aneurysm located along the internal carotid artery. The target aneurysm must have the following characteristics to be treated as part of the study:
 - Aneurysms with a neck \geq 4mm or no discernible neck and a size (maximum fundus diameter) of $>$ 10mm;
 - The parent artery must have a diameter of 2.0-5.0mm distal and/or proximal to the target intracranial aneurysm (IA)
 - Subject is a poor candidate for open surgical treatment because of prior surgical procedures, comorbidities or location limiting conventional surgical options and has a target aneurysm with a maximum fundus diameter less than 10 mm but $>$ 7 mm with ANY of the following morphologies:
 - segmental parent artery dysplasia
 - aneurysm neck involving $>$ 180 degrees of parent artery circumference
 - complex lobulations limiting stent/coiling as a treatment option
 - neck \geq 4mm or no discernable AND dome/neck ratio $<$ 2
- Fusiform aneurysms of any size requiring treatment;
- Subjects who have signed an informed consent form (ICF) and meet all the clinical and angiographic inclusion criteria set forth for this study

The treatment of aneurysms will be located in the following zones:

Zone	Anatomy Included	Additional Criteria
1	Petrous through superior hypophyseal segments of the ICA	• None
2	Communicating segment of the ICA through A1 or M1 segment	• exclude bifurcation aneurysms
3	Posterior Circulation including:	• exclude bifurcation aneurysms • exclude large or giant dolichoectatic aneurysms

5.5 Study Endpoints and Success Criteria

Primary Endpoint(s):

1. The primary safety endpoint will consist of a composite of any/all of the events list below:

- death or major stroke within 30 days post procedure
- neurological death or major ipsilateral stroke within 12 months post procedure, measured by mRS and NIHSS.

NOTE: A major stroke is defined as a new neurological event that persists for > 24 hours and results in a ≥ 4 point increase in the NIHSS score compared to baseline or compared to any subsequent lower score. A minor stroke is defined as a new neurological event that persists for > 24 hours and results in an increase of < 4 points in the NIHSS score compared to baseline or compared to any subsequent lower score.

- A major ipsilateral stroke is defined as that occurring within the vascular distribution of the stented artery
- Neurologic death is defined as a death which has been adjudicated by an independent clinical events committee to have directly resulted from a neurologic cause

Neurological and functional assessments will be measured by comparing baseline scores at 30 days, 180 days and 12 months post procedure.

2. The primary effectiveness endpoint is:

Proportion of subjects with complete occlusion (100% occlusion) of the target aneurysm and $\leq 50\%$ stenosis of the parent artery at the target IA at 12 months as assessed by angiography and in whom an alternative treatment of the target IA had not been performed. An alternative treatment is defined as re-treatment of the target aneurysm with an alternative treatment modality including open repair, endovascular placement of an additional stent or treatment of In-stent Stenosis observed at the 180 day or 12 month follow-up time-points or at an unscheduled study follow up visit.

Secondary Endpoint(s):

1. Proportion of subjects with clinically acceptable (90-100%) occlusion of the target aneurysm, $\leq 50\%$ stenosis of the parent artery at the target IA at 12 months (+ 60 days, - 30 days) as assessed by angiography, and in whom an unplanned alternative treatment of the target IA had not been performed within 12 months. An alternative treatment is defined as re-treatment of the target aneurysm with an alternative treatment modality including open repair, endovascular placement of an additional stent or treatment of In-stent Stenosis observed at the 180 day or 12 month follow-up time-points or at an unscheduled study follow up visit.
2. Proportion of subjects in whom an alternative treatment of the target IA had not been performed within 12 months
3. Proportions of subjects with clinically acceptable aneurysm occlusion (90 %-100 %) of the target aneurysm at 12 months (+ 60 days, -30 days)
4. Incidence of $\geq 50\%$ In-Stent Stenosis(ISS)at the target IA at 12 months as assessed by angiography at an independent corelab

5. Proportion of subjects with complete occlusion of the target aneurysm on 12-month angiography(+ 60 days, -30 days)
6. Incidence of FRED System procedure related Serious Adverse Events
7. Incidence of FRED System device related Serious Adverse Events;
8. Incidence of unsuccessful delivery of the FRED device
9. Incidence of unsuccessful deployment of the FRED device
10. Incidence of migration of the FRED device at 12 months
11. Unplanned alternative treatment on the target IA within 12 months defined as re-treatment of the target aneurysm with an alternative treatment modality including open repair, endovascular placement of an additional stent or treatment of In-stent Stenosis observed at the 180 day or 12 month follow-up time-points or at an unscheduled study follow up visit.
12. Incidence of change in clinical and functional outcomes at 180 days and 1 year follow up, as measured by an ≥ 3 point increase in the modified Rankin Scale due to neurologic disability as compared to baseline
13. Incidence of major stroke, as measured by NIHSS at 12-months (and ophthalmic examination related to the target aneurysm if determined appropriate)
14. Incidence of minor stroke, as measured by NIHSS at 12-months (and ophthalmic examination related to the target aneurysm if determined appropriate)

The statistical analyses of the primary and secondary endpoints of the study will be based on imaging data that has been reviewed and assessed by an independent core lab and on trial clinical data that has been reviewed and adjudicated by the independent Clinical Events Committee (CEC).

Study Success Criteria:

The criterion for success is based on the posterior probability of the alternative hypotheses for both efficacy and safety (i.e. both efficacy and safety being met).

Efficacy Criterion

The FRED System will be declared efficacious if the posterior probability of the alternative hypothesis H_A based on the primary efficacy endpoint for is large, that is

$$P(H_A|Data) = P(\pi_e > 45\%|Data) > \pi^*$$

where π^* is the level of evidence we require to declare the efficacy alternative hypothesis true.

Safety Criterion

The FRED System will be declared safe if the posterior probability of the alternative hypothesis H_A based on the primary safety endpoint for is large, that is

$$P(H_A|Data) = P(\pi_s < 25\%|Data) > \pi^*$$

where π^* is the level of evidence we require to declare the safety alternative hypothesis true.

For both safety and efficacy criterion, the posterior probability bound is

$$\pi^* = 0.95.$$

5.6 Subject Enrollment

195 subjects will be enrolled in the study at up to 30 investigational sites located in the United States and Japan. Additional subjects may be added to reach 155 subjects with a 12 month follow-up evaluation.

5.7 Study Duration

The enrollment period is estimated to be 12 – 36 months from the date of study commencement. Data from 195 patients, who undergo treatment with the FRED Implant System with complete 12 month follow-up will be analyzed and summarized. It is anticipated that the data will be submitted to FDA in an original Premarket Approval Application (PMA). The duration of the clinical study from first enrollment through regulatory approval is estimated to be 36-42 months. MicroVention may also request enrollment of additional patients under a Continued Access Protocol, i.e., extended investigation, throughout the preparation of the PMA and regulatory approval process

5.8 Inclusion Criteria

Subjects for this study must meet ALL of the following criteria:

- Subject whose age is ≥ 22 and ≤ 75 years;
- Subject has a single target aneurysm located in the following zones:
 - Zone 1 - Petrous through superior hypophyseal segments of the ICA
 - Zone 2 - Communicating segment of the ICA through A1 or M1 segment
 - Zone 3 - Posterior Circulation
 - Basilar artery (not including the basilar bifurcation)
 - Vertebral artery (distal to the PICA)
 - Vertebral artery (proximal to the PICA)

AND fit any of the following criteria:

- Subject for whom existing endovascular options (coiling, stent-assisted coiling) would be ineffective because the aneurysm is predisposed to recurrence to having any of the following characteristics:
 - a) Aneurysm has a maximum fundus diameter less than 10mm but ≥ 2 mm.
 - i. To mitigate the risk for the treatment of subjects with small stable aneurysms that may not require treatment with respect to the possible risks and benefits associated with treatment, the treating clinician shall record a treatment justification (such as increased risk of rupture) for the aneurysms < 7 mm that have been selected for treatment
 - b) Aneurysm has any of the following morphologies:
 - i. no discernible neck.
 - ii. segmental parent artery dysplasia.
 - iii. Aneurysm neck involving > 180 degrees of parent artery circumference.
 - iv. Complex lobulations limiting stent/coiling as a treatment option
 - v. Neck > 4 mm or dome/neck ratio ≤ 2 .
- OR**
- Subject has a fusiform aneurysm of any size requiring treatment.
- OR**
- Subject is a poor candidate for open surgical treatment because of prior surgical procedures, comorbidities or location limiting conventional surgical options

The parent artery diameter must be 2.0 - 5.0mm distal and/or proximal to the target intracranial aneurysm;

Subject fulfills study requirements, and the subject or his/her Legally Authorized Representative provides a signed informed consent form;

Negative pregnancy test (serum or urine) in a female subject who has had menses in the last 18 months;

Subject commits to return to the investigational site for the 30-day, 180-day, and 12-month follow-up evaluations.

A subject is considered to be enrolled after signing the Informed Consent Form.

Given the epidemiology and clinical prevalence of intracranial aneurysms, it is expected that up to 80% of the patients treated will present with anterior circulation aneurysms and up to 20% of the patients will present with posterior circulation aneurysms.

5.9 Exclusion Criteria

Subjects **shall be excluded** from the study if **ANY** of the following conditions exist:

- Subject who suffers from a subarachnoid hemorrhage in the last 60 days
- Subject who suffers from any intracranial hemorrhage in the last 30 days
- Subject who presents with an intracranial mass or currently undergoing radiation therapy for carcinoma or sarcoma of the head or neck region;
- Subject with symptomatic extracranial or intracranial stenosis of the parent artery (>50%) proximal to the target aneurysm;
- Subject with an irreversible bleeding disorder, a platelet count of less than 100,000/ml < 100 x10³ cells/mm³ or known platelet dysfunction or a contraindication to or inability to tolerate anticoagulants/antiplatelet agents;
- Active peptic ulcer disease, major systemic hemorrhage within 30 days, active bleeding diathesis, platelet < 100,000 or known platelet dysfunction, INR ≥ 1.5, clotting factor abnormality, current alcohol or substance abuse, uncontrolled severe hypertension (systolic pressure >180 mm Hg or diastolic pressure >115 mmHg), creatinine ≥ 3.0 mg/dL (unless on dialysis);
- Subject with contraindications or known allergies to anticoagulants or antiplatelets (aspirin, heparin, ticlopidine, clopidogrel, prasugrel or ticagrelor);
- Subject with known hypersensitivity to metal, such as nickel-titanium and metal jewelry
- Subject with documented contrast allergy, or other condition, that prohibits imaging.
- Evidence of active infection at the time of treatment;
- Presence of any of the following unequivocal cardiac sources of embolism; chronic or paroxysmal atrial fibrillation, mitral stenosis, mechanical valve, endocarditis, intracardiac clot or vegetation, myocardial infarction within three months, dilated cardiomyopathy, left atrial spontaneous echo contrast, ejection fraction less than 30%;
- Subject who has had a previous intracranial stenting procedure associated with the target aneurysm;
- Subject who is unable to complete the required follow-ups;
- Subject with life-threatening diseases;
- Subject who is pregnant or breastfeeding;
- Subject of childbearing potential, and unwilling to prevent pregnancy during their participation in the study

5.10 Angiographic Exclusion Criteria

- Subject has a cerebral diagnostic angiogram that demonstrates an aneurysm that is not appropriate for endovascular treatment;
- Subject has extracranial stenosis greater than 50% in the carotid artery of the target aneurysm;
- Subject has intracranial stenosis greater than 50% in the treated vessel;
- Subject has a mycotic or dissecting aneurysm;
- Subject has a bifurcation aneurysm for example at the bifurcation of the internal carotid artery, the middle cerebral artery or at the anterior communicating artery such that placement of the device would fail to satisfactorily cover the entire neck of the aneurysm or a major cerebral artery would be put at risk through "jailing";
- Subject has a posterior circulation aneurysm with the following morphology:
 - Placement of device would include basilar artery bifurcation
 - Large or giant dolichoectatic aneurysm;
- Subject's aneurysm has significant branch exiting from dome of aneurysm (for example, ophthalmic artery);
- Subject is harboring more than one aneurysm with both aneurysms requiring treatment at the same time;
- Subject has an arteriovenous malformation (AVM) in the area of the target aneurysm.

5.11 Follow-Up

All subjects enrolled into the study and treated with the FRED System shall be followed at 30 day (± 7 days), 180 days (± 30 days), and 12 months (+ 60 days, -30 days). The follow-up visits will include an examination by a study investigator, according to the criteria below:

30 Day Visit (+/- 7 days)

- A physical, functional, and neurological examination, using the NIH Stroke Scale Score and Modified Rankin Scale. The information shall be collected on the 30 Day Follow-up CRF worksheets

180 days Visit (+/- 30 days)

- A physical, functional, and neurological examination including the NIHSS Stroke Scale Score and Modified Rankin Scale. A neuro-ophthalmic examination may be requested if a baseline exam was performed. The information shall be entered on the 180 days Follow-up CRF worksheets
- Angiography (all required imaging to be sent to Core Laboratory to include AP, lateral and working positions angiograms. The investigator should take proper steps to ensure that follow-ups angiograms are performed using similar views.

12 Month Visit (+ 60 days, - 30 days)

- A physical, functional, and neurological examination including the NIH Stroke Scale Score and Modified Rankin Scale. The information shall be entered on the 12 Month Follow-up CRF worksheets
- Angiography (all required imaging to be sent to Core Laboratory to include AP, lateral and working positions angiograms). The investigator should take proper steps to ensure that follow-up angiograms are performed using similar views.

Unscheduled Visits

- Subjects shall be seen and assessed by members of the neurovascular team throughout the study period. If any events occur or if any imaging is performed outside the follow-up schedule, the information shall be captured and reported on the Unscheduled Visit CRF.

6.0 Statistical Methods

6.1 Analysis Population

The statistical analysis will use four populations:

- 1) The Intent to Treat (ITT) population will consist of all enrolled subjects who had an introduction of the FRED Implant System and were followed for 12 months or failing prior to 12 months. The ITT population will be used for all effectiveness analyses to test the efficacy hypothesis.
- 2) The Safety Population will consist of all subjects in whom the investigational device was implanted as well as deaths due to technical failures during the index procedure. The Safety Population will be used to test the safety hypothesis.
- 3) The Per Protocol Population will consist of all subjects in the ITT Population for whom there were no major protocol deviations.*

* Major protocol deviations include subjects who failed any of the inclusion/exclusion criteria, who were not evaluated within the study windows, or who received a treatment intervention impacting the ability to evaluate either safety or efficacy

The primary and secondary effectiveness endpoints will also be evaluated for the Per Protocol Population.

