 - If the FRED Device cannot be deployed due to any other issues related to the procedure, the Subject will be counted as enrolled but not treated and will not be considered a secondary endpoint failure. The Subject will be maintained within the study for one (1) week. Thereafter, the Subject may be replaced in the study. The Subject will be monitored for any Adverse Event for one (1) week following the failed deployment due to issues related to the procedure. If the Subject has an Adverse Event, that Subject will also have 30-day, 6-month and 12-month clinical follow-ups. An angiographic follow-up will not be required unless the clinician believes it is medically necessary. Unless medically necessary to pursue treatment sooner, it is recommended that further attempts to treat the target aneurysm be deferred for a minimum of one (1) week so that any potential procedural Adverse Events may be monitored.

Subgroup Analysis

Results for the primary and secondary endpoints will be stratified by the following subgroups:

- Location (anterior, posterior)
- Age (<55, 55-64, ≥65)
- Gender: results will be stratified by gender
- Anatomic location (zone 1, 2 and 3)
- Region (Japan, other countries)

Since it is not possible to determine any observed differences are truly due to a difference in treatment effect, any observed significant differences in outcomes ($p < 0.1$) across subgroups will be examined and compared to available literature regarding known risk effects for the subgroups.

Missing Data

In general, all analyses will be performed using the ITT analysis set, which constitutes all available cases and all available visits. Every effort will be made to get 12 month follow-up for all study patients. The primary endpoints will be analyzed first without imputing missing or incomplete data. Multiple sensitivity analyses will be performed in order to better understand the potential effect of missing or incomplete data on the conclusions for the primary endpoints. These sensitivity analyses will impute values for subjects who are event free (for the specific primary endpoint), but do not have complete data. The analysis method used on the imputed datasets will use the binary result (i.e. simple event percents).

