Study Design	
A multi-center, prospective, single-arm study with follow-up at discharge, 30 days (± 7 days), 180 days (± 30 days) and 12 months (+ 60 days, -30 days). Data will be analyzed according to nominal visit, e.g. 30 days, 180 days, 12 months as opposed to actual date.
 
The intent-to-treat (ITT) population as defined below will be the primary population for all efficacy analyses and the safety population for all safety analyses. One hundred forty-five (145) subjects will constitute the ITT cohort, which is identical to the Safety cohort. These subjects were enrolled and treated at 23 sites located in United States and Japan.
 
Subjects are included in study analyses consistent with the prospective literature control, with efficacy and safety objective performance criteria (OPCs) used to determine sample size.
 
Two OPC sets will be considered in support of efficacy and safety as per the original protocol (primary) as well as more strict (supportive) OPCs as follows:
 
 • Primary: Original PG specified in the protocol (45% for efficacy and 25% for safety) • Supportive: Updated PG presented to FDA at the Feb 2017 meeting (46% for efficacy and 15% for Safety). 
Study success is defined as achieving statistical significance for the primary OPCs.
 
Primary Analyses: The powers will be 80% to rule out a 45% OPC (efficacy) margin (lower bound) and 80% to rule out a 25% OPC (safety) margin (upper bound) using one-sided tests. The trial will be considered successful if the one-sided 95% credible lower bound of the efficacy rate exceeds the 45% OPC and the one-sided 95% credible upper bound of the safety rate is below the 25% OPC. The use of one-sided testing is consistent with the protocol.
 
Supportive Analyses: The powers will be 90% to rule out a 46% OPC (efficacy) margin (lower bound) and 90% to rule out a 15% OPC (safety) margin (upper bound) using two-sided tests. The trial will be considered successful if the two-sided 95% credible lower bound of the efficacy rate exceeds the 46% OPC and the two-sided 95% credible upper bound of the safety rate is below the 15% OPC. The use of two-sided testing is consistent with the PIPELINE PMA and FDA guidance.

Follow-Up Schedule	All enrolled and treated subjects had follow up scheduled at 30 day (± 7 days), 180 days (± 30 days), and 12 months (+ 60 days, -30 days).
Interim Analyses	No interim analysis are planned.

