5 ANALYSIS POPULATIONS

The statistical analysis will use three populations:

- 1) The Intent to Treat (ITT) population will consist of all enrolled subjects who had an introduction of the FRED Implant System into the bloodstream. The ITT population will be used for all effectiveness analyses to test the efficacy hypothesis for both OPC sets.
- 2) The Safety Population will consist of all subjects in whom the investigational device was implanted as well as deaths due to technical failures during the index procedure. The Safety Population will be used to test the safety hypothesis for both OPC sets.
- 3) The Per Protocol Population will consist of all subjects in the ITT Population for whom there were no major protocol deviations. All protocol deviations will be assessed by the Clinical Events Committee.

The primary and secondary effectiveness endpoints will also be evaluated for the Per Protocol Population.

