7 ENDPOINT ANALYSES

7.1 PRIMARY EFFICACY VARIABLE

The primary efficacy endpoint is the percent of subjects in the ITT population with complete occlusion (defined as Raymond class I) without clinically significant stenosis (defined as $\geq 50\%$ stenosis) of the parent artery at the target IA based on core lab evaluations at the 12-month follow-up angiography and in whom an alternative treatment of the target IA had not been performed post-FRED placement. An alternative treatment is defined as re-treatment of the target aneurysm with an alternative treatment modality including open repair, endovascular

placement of an additional stent or treatment of In-stent Stenosis observed at the 180-day or 12 month follow-up time-points or at an unscheduled study follow up visit.

The primary efficacy hypotheses are:

$$H_{E0}: \pi_E \leq 0.45$$

$$H_{E1}: \pi_E > 0.45$$

The null hypothesis (H_{E0}) for this endpoint states that the true proportion of subjects treated with the FRED Device who achieve complete occlusion (Raymond class I) without clinically significant ($\geq 50\%$) stenosis of the parent artery 12 months post-treatment and without any subsequent alternative treatment is no higher than 45%. The alternative hypothesis the FRED trial aims to demonstrate is that the true proportion of subjects who achieve effectiveness success at 12 months is greater than 45%.

Using the prior

$$\pi_E \sim Beta(1,1)$$

the posterior distribution for the primary efficacy endpoint rate will be

$$\pi_E | E, n \sim Beta(1 + E, 1 + n - E)$$

where n is the number of evaluable subjects and E is the number of subjects who meet the efficacy endpoint. The point estimate of the posterior distribution of the primary efficacy endpoint will be presented with its lower 95% credible bound, as well as the posterior probability of the alternative hypothesis H_{E1} . If the posterior probability exceeds 0.95, the primary efficacy endpoint will have been met.

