7.2 PRIMARY SAFETY ENDPOINT

The study's primary safety endpoint is the proportion of subjects in the Safety Population who experience either major stroke or death within 30 days, or major ipsilateral stroke or neurological death 31 days through 12 months post procedure. CEC-adjudicated data will be used for this analysis.

The primary safety hypotheses are:

$$H_{S0}: \pi_S \geq 0.25$$

$$H_{S1}: \pi_S < 0.25$$

The null hypothesis (H_{S0}) for this endpoint states that the true proportion of subjects treated with the FRED Device who experience neurologic death or major ipsilateral stroke one-year post-treatment is equal to or higher than 25%. The alternative hypothesis the FRED trial aims to demonstrate is that the true proportion of subjects treated with the FRED Device who experience neurologic death or major ipsilateral stroke one-year post-treatment is actually lower than 25%.

Using the noninformative prior

$$\pi_S \sim \text{Beta}(1,1)$$

the posterior distribution for the primary safety endpoint event rate will be

$$\pi_S | S, n \sim \text{Beta}(1 + S, 1 + n - S)$$

where n is the number of evaluable subjects and S is the number of subjects who meet the safety endpoint. The point estimate of the posterior distribution of the primary safety endpoint will be presented with its lower 95% credible bound, as well as the posterior probability of the alternative hypothesis H_{S1} . If the posterior probability exceeds 0.95, the primary safety endpoint will have been met

The supportive analysis (second OPC set) will be conducted for both primary efficacy and primary safety using more restrictive performance goals identified from a revised set of literature analysis and presented to FDA on 16 February 2017. The format of this analysis will be a Bayesian design identical in form to the above except that the performance goals will be 0.46 for efficacy and 0.15 for safety. Details of the resulting analyses and associated power are as below, from which it can be seen that the study is sufficiently powered at the final enrolled and treated count of 140.

	Efficacy		Safety	
	Original	Revised	Original	Revised
Significance level, alpha	0.05	0.025	0.05	0.025
1 or 2-sided test	1	1	1	1
Null: OPC, p_0	0.45	0.46	0.25	0.15
Alternative: FRED, p_A	0.58	0.60	0.15	0.06
Power (%)	90	90	90	92
N	140	140	140	140

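### The SAP's primary efficacy denominator contradicts itself, and its imputation rule lets a subject who died be scored a 12-month success

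*Protocol*

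**What the plan says.** **Population.** Protocol 6.1 takes "all enrolled subjects who had an introduction of the FRED Implant System and were followed for 12 months or failing prior to 12 months". SAP 5 takes "all enrolled subjects who had an introduction of the FRED Implant System into the bloodstream", with no follow-up condition. Protocol 5.1 leaves analysis detail to the SAP, and SAP 1 makes the SAP's own ITT set the primary efficacy population.

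**Denominator.** SAP 7.1 defines the endpoint as "the percent of subjects in the ITT population with complete occlusion" (and the other components). The posterior in the same section is Beta(1+E, 1+n−E), "where n is the number of evaluable subjects and E is the number of subjects who meet the efficacy endpoint". Neither document defines evaluable; Protocol 6.2 uses the word in the same way. SAP 6.3, in a paragraph on descriptive statistics, bases proportions on non-missing values only.

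**Counts.** SAP 1: "One hundred forty-five (145) subjects will constitute the ITT cohort, which is identical to the Safety cohort". It describes these subjects as enrolled and treated. SAP 7.2: "the study is sufficiently powered at the final enrolled and treated count of 140".

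**Missing outcomes.** Protocol 6.2: "The primary endpoints will be analyzed first without imputing missing or incomplete data"; imputation belongs to its sensitivity analyses. SAP 6.6 imputes the outcome judged most likely for any subject who lacks the 12-month evaluations. If that cannot be done, it falls back on probabilities conditional on the 6-month outcome. Subjects with no follow-up data are not imputed, and it is not said whether they stay in n. SAP 7.3 fills missing 12-month occlusion from the 180-day result. None of these rules mentions death, and neither does the list of efficacy failures in Protocol 6.2.

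**The concern.** This is a single-arm test against a fixed 45% goal. There is no control arm in which a denominator choice could cancel out, so both n and the score given to a death enter the decision directly.

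On the text of SAP 7.1, 6.3, 6.6 and 7.3, a subject who died at month nine with an occluded aneurysm at day 180 could be left out of n, imputed a success, given a success probability, or counted as a non-success. The imputation rule is more than a missing detail: read literally, it assigns 12-month occlusion to someone who could not have had a 12-month angiogram. The SAP also does not say whether the imputed or the unimputed analysis decides study success.

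**Working it through.** **Inputs.** Goal 45%, Beta(1,1) prior, success if the posterior probability exceeds 0.95 (SAP 7.1). Counts 145 (SAP 1) and 140 (SAP 7.2). Planned true rates 56.5% (Protocol 6.2) and 58% (SAP 7.2 table). Numbers of deaths are not in the documents and are assumed.

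**1. The plan's own figure.** SAP 7.2 gives 90% power for 45% against 58% at N=140, one-sided 0.05. An exact binomial test needs at least 74 successes: P(Bin(140, 0.45) ≥ 74) = 3.8% and P(Bin(140, 0.58) ≥ 74) = 90.6%. The figure reproduces. The planned posterior rule needs 73, with type I error 5.4% and power 93.1%.

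**2. Threshold for each count.** Find the smallest E with P(π > 0.45 | Beta(1+E, 1+n−E)) > 0.95.

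| Successes E | Posterior, n=140 | Posterior, n=145 |
|---|---|---|
| 73 | 0.955 | 0.903 |
| 74 | 0.969 | 0.928 |
| 75 | 0.979 | 0.948 |
| 76 | 0.986 | 0.963 |

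The rule needs 73/140 (52.1%) or 76/145 (52.4%).

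**3. One death among 145 (assumed), with 75 successes observed in the other 144.**

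- Death as non-success: 75/145, posterior 0.948, fails.
- Death excluded: 75/144, posterior 0.956, passes.
- Death imputed a success: 76/145, posterior 0.963, passes.

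**4. How often 140 or 145 matters.** Let E be the successes among 140 and k those among the five extra subjects.

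- Five succeed at the common rate p. Pass at 140 and fail at 145 is P(E ≥ 73 and E+k ≤ 75), with E ~ Bin(140, p) and k ~ Bin(5, p): 2.1% at p=56.5%, 1.3% at 58%. The reverse, P(E ≤ 72 and E+k ≥ 76), is 1.1% and 0.7%.
- All five are non-successes, overall rate p held over 145. Then E ~ Bin(140, p×145/140), and the chance is P(73 ≤ E ≤ 75): 8.2% at p=56.5% (0.565×145/140 = 0.585), 4.6% at 58% (0.601).

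**5. Type I error, conditional on what the 45% goal refers to.**

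- Goal over all treated subjects, three non-successes removed from 145: the rate among the remaining 142 is 0.45×145/142 = 0.4595, the threshold is 74, and P(Bin(142, 0.4595) ≥ 74) = 8.3%. With none removed it is P(Bin(145, 0.45) ≥ 76) = 4.4%.
- Goal over evaluable subjects: P(Bin(n, 0.45) ≥ threshold) lies between 4.4% and 5.5% for every n from 135 to 145, so there is no inflation.

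**The case against.** Much of the case against stands.

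- **The SAP governs.** A reader might infer from Protocol 6.1 alone that the analysis set is undecided. The documents do not support that: SAP 5 is clear, and SAP 2 settles undeployed devices, on which Protocol 6.2 is inconsistent. With ITT and safety sets stated as identical, few such subjects could be affected. These differences are protocol alignment.
- **The imputation rules form a hierarchy.** The second paragraph of SAP 6.6 orders subject-level imputation before the conditional probability, and SAP 7.3 describes much the same conditional step. The gap is the absence of a rule for death and of a stated primary or sensitivity status.
- **The 140 sits in a power statement.** No text makes it the analysis n. It is nevertheless called the final enrolled and treated count, which conflicts with 145.
- **73 to 75 successes.** A reader might infer from the table that such a result simply passes on one count and fails on the other. That requires all five extra subjects to be non-successes, which nothing in the documents shows.
- **Inflated type I error.** A reader might infer this too. It depends on the goal being a rate over all treated subjects. The documents do not state how the literature denominators were formed, and SAP 1 says "Subjects are included in study analyses consistent with the prospective literature control".
- **Percent of ITT already makes a death a non-success.** This is a fair reading of one sentence in SAP 7.1, but the next definition of n and SAP 6.6 permit others.
- **Worst-case (Protocol 6.2) and tipping-point (SAP 7.3) analyses are planned.** They would reveal any dependence but do not decide success.

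**Conclusion.** The concern holds, within the SAP and in narrow form. SAP 7.1 gives two denominators, SAP 1 and 7.2 give two counts, and the imputation rule as written covers deaths. That textual finding needs no assumption.

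The numerical effect is real but local. One assumed death can change the verdict when about 52% of subjects succeed. For a handful of affected subjects, a result well above that is the same under every reading. The step 4 probabilities assume either typical or uniformly unsuccessful extra subjects; the documents do not say which is nearer. An error rate above nominal is a conditional possibility only, because the basis of the 45% goal is not given. The issue is worth correcting before outcomes are analysed, since SAP 9.4 requires approval by then and an approved text with these rules would still leave the choice open.

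**What to change.** Wording only; no new data.

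- **SAP 7.1:** set n to all subjects in the SAP 5 ITT population. Reconcile 145 with 140. Make the non-missing rule in SAP 6.3 consistent with this.
- **SAP 6.6 and 7.3:** state that death before the 12-month assessment is a non-success in the primary analysis and is not imputed. Treat late, unrelated deaths after documented occlusion differently in a sensitivity analysis. Say whether subjects with no follow-up data stay in n.
- **Status:** state whether the SAP 6.6 hierarchy is the primary analysis or a sensitivity analysis, given that Protocol 6.2 puts the unimputed analysis first.
- **Goal:** state whether the 45% was built on treated or evaluable subjects.
- **Protocol 6.1 and 6.2 (technical failures):** align with SAP 2 and 5.

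Cost: a slightly less favourable success rate. Scoring deaths as non-successes is one choice of estimand, and it is conservative if the goal was built on evaluable subjects. The treatment of exactly 50% stenosis, a failure in SAP 7.1 but not in SAP 3.2 or the protocol's primary endpoint, is a separate item.
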